PROTOCOL SUMMARY:

Long title: Convalescent Plasma to Limit Coronavirus Associated Complications: A Randomized Open label, Phase 1 Study Comparing the Efficacy and Safety of High-Titer Anti-SARS-CoV-2 plasma vs. placebo in hospitalized patients with interstitial pneumonia due to COVID-19

Short title: CSSC-002

Clinical Phase: 1

IND Sponsor: Johns Hopkins via a national IND

Conducted by: Mayo Clinic in collaboration with Johns Hopkins University, Washington University in St. Louis and other interested parties.

Sample Size: 20

Study Population: Hospitalized COVID-19 patients aged 18 years of age with respiratory symptoms within 3 to 7 days from the beginning of illness.

Study Duration: April 1, 2020 to December 31, 2022

Study Design: This randomized placebo-controlled open label phase 1 trial will assess the efficacy and safety of anti-SARS-CoV-2 convalescent plasma in hospitalized patients with acute respiratory symptoms between 3 and 7 days after the onset of symptoms with or without confirmed interstitial COVID-19 pneumonia by chest CT. A total of 20 eligible subjects will be randomized in a 1:1 ratio to receive either high titer anti-SARS-CoV-2 plasma or control (standard thawed plasma)

The following will be assessed in all subjects:

- Age, sex, comorbidities, date of symptoms, source of infection, type of admission, APACHE score, SOFA score, Clinical status, vital signs including temperature, respiratory rate, oxygen saturation, oxygen requirement, CBC with neutrophil counts, lymphocytes count, CRP, chest x-ray, chest CT, location in hospital,
- Safety and efficacy: Day 0 (baseline), 1, 2, 3, 7, 14, and 28 and once monthly at 2-3 months.
- Serum or plasma antibody titer₁ to SARS-CoV-2: Day 0, 1, 3, 7, 14 (additional days 21 and 28 may be included, as available)

¹ Measured via initial anti-SARS-CoV-2 ELISA and serum neutralizing antibody titer to SARS-CoV-2.

- SARS-CoV-2 PCR from nasopharyngeal swabs: Day 0, 3, 7, 14 and at any time when there is clinical suspicion for COVID-19
- Outcome measures: increased O2 requirement (PaO2/FiO2 ratio or SpO2/Flo2), supplemental oxygen strategy (nasal cannula, , high flow nasal cannula, noninvasive ventilation, intubation and invasive mechanical ventilation, rescue ventilation i.e. neuromuscular blocking agents, prone positioning, corticosteroids, ECMO), vasopressors, renal support, ICU LOS, ICU mortality, Hospital LOS, Hospital mortality, 28 day mortality

Study Agent:

- Pathogen reduced SARS-CoV-2 convalescent plasma (1-2 units; ~300-600 mL at neutralization antibody titer >1:64 *if possible* >1:160 *this is a moving target as assays develop*)
- Standard plasma²

Primary Efficacy Objective: Reduction in progression of oxygenation and ventilation support

Primary Endpoint: Avoidance of ICU admission.

Secondary endpoints:

1. Cardio-circulatory arrest (at any time)
2. Transfer to ICU
3. Type and duration of respiratory support (and other ICU support)in ICU
4. ICU mortality and LOS
5. Hospital mortality and LOS
6. Ventilator-free days
7. 28 day mortality

Primary Safety Objective: Evaluate the safety of treatment with high-titer anti-SARS-CoV-2 plasma versus control (standard plasma) in hospitalized patients with COVID-19 respiratory symptoms.

Primary Safety Endpoints:

1. Rapid deterioration of respiratory or clinical status on transfusion of SARS-CoV-2 convalescent plasma
2. Cumulative incidence of serious adverse events during the study period: transfusion reaction (fever, rash), transfusion related acute lung injury (TRALI), transfusion associated circulatory overload (TACO), transfusion related infection

² Solvent detergent treated pooled plasma

Secondary Objectives:

1. Compare the anti-SARS-CoV-2 convalescent plasma and control (standard plasma) groups anti-SARS-CoV-2 titers at days 0, 1, 3, 7 and 14 (additional days 21 and 28 may be included, as available).
2. Compare the rates, levels and duration of SARS-CoV-2 RNA in NP swabs using RT-PCR amongst the anti-SARS-CoV-2 convalescent plasma and control (standard plasma) groups at days 0, 3, 7 and 14. Other specimen types may be tested as available (eg., BAL fluid, tracheal secretions, sputum, etc.) or when RT-PCR assays are validated for additional sources (*i.e.*, stool, blood).

Study population:

Inclusion Criteria for Enrollment

1. Patients must be 18 years of age or older
2. Hospitalized with COVID-19 respiratory symptoms and confirmation via COVID-19 SARS-CoV-2 RT-PCR testing. Patient is willing and able to provide written informed consent and comply with all protocol requirements.
3. Patient agrees to storage of specimens for future testing.
4. If female must not be pregnant and/or breastfeeding.

Exclusion Criteria

1. Female subjects with positive pregnancy test, breastfeeding, or planning to become pregnant/breastfeed during the study period
2. Receipt of pooled immunoglobulin in past 30 days
3. Contraindication to transfusion or history of prior reactions to transfusion blood products

INCUBATION PERIOD AND ONSET OF SYMPTOMS 3 DAYS AGO		FIRST WEEK				SECOND WEEK				LONG TERM INFO PENDING
		WARD Illness day 4	WARD Illness day 5	WARD Illness day 6	WARD Illness day 7	WARD/ICU Illness day 8	ICU Illness day 9	ICU Illness day 10	ICU Illness day 11	
Typical features according to current publications Age Mean (SD) 55.5 (13-1), Male (68%) Exposure to Huanan seafood market in Wuhan, China (49%) Chronic medical underlying illness (51%) Admission to Intensive Care Unit (23%)										
REPEATED SAMPLING OF THE NASOPHARYNX AND TRACHEAL ASPIRATES (IF INTUBATED) BY rRT-PCR FOR THE COVID-19		Initial important viral shedding		Decrease of the viral shedding sometimes associated with transient respiratory deterioration		Respiratory failure, increase of the viral shedding and viremia or Decrease of the viral shedding, and superinfections		Duration of viral excretion unknown		
OXYGEN THERAPY AND MECHANICAL VENTILATION		NO		Consider oxygen support	FNC	FNC followed by MV	MV		MV	
ORGAN FAILURE		Typical signs according to current publications Fever, cough, and shortness of breath (15%) bilateral pneumonia (75%), lymphopenia (35%), thrombocytopenia (12%), prothrombin time decreased (30%), elevated liver enzyme levels (about 30%)		Deterioration of respiratory status with most often spontaneous recovery		ARDS If shock beware of superinfections ⚠️ Possible renal failure Neurological failure unlikely Hemostasis disorders		YES		
CO-INFECTION/SUPERINFECTION		NOT LIKELY				Consider a possible HAP/VAP and other nosocomial infections (see text for diagnostic procedures)		Profound immune paralysis and late onset infections		
ANTIBIOTICS		NO				Consider antibiotic therapy		YES		
ANTIVIRAL AGENTS		NO				Consider antiviral agents if deterioration ^a				

FNC = flow nasal cannula; HFNC = high flow nasal cannula; HAP = healthcare-associated pneumonia; VAP = ventilator-associated pneumonia; MV = Mechanical ventilation;
^a The use of immunomodulation including corticosteroids is unlikely but debated

Figure 1 (from Bouadma et al Int Care Med 2020) describes what is known about the potential patient course of COVID-19 pneumonia. Our goal is to intervene in the middle of “green” area and improve patient status and avoid ICU admission.

LIST OF ABBREVIATIONS

ADR: Adverse Drug Reaction
ADE: Antibody-mediated enhancement of infection
AE: Adverse Event/Adverse Experience
CDC: United States Centers for Disease Control and Prevention
CFR: Code of Federal Regulations
CLIA: Clinical Laboratory Improvement Amendment of 1988
COI: Conflict of Interest
COVID-19: Coronavirus Disease
CRF: Case Report Form
DMC: Data Management Center
DSMB: Data and Safety Monitoring Board
EUA: Emergency Use Authorization
FDA: Food and Drug Administration
GCP: Good Clinical Practice
HBV: Hepatitis B virus
HCV: Hepatitis C virus
HIV: Human immunodeficiency virus
HTLV: Human T-cell lymphotropic virus
IB: Investigator's Brochure
ICF: Informed Consent (Informed Consent Form)
ICH: International Conference on Harmonization
ICU: Intensive Care Unit
IEC :Independent ethics committee
IND: Investigational New Drug Application
IRB: Institutional review board
ISBT: International Society of Blood Transfusion
ISM: Independent Safety Monitor
IWRS :Interactive web response system
MERS: Middle East Respiratory Syndrome
NA: Nuclear antibody
NP: Nasopharyngeal
OP: Oropharyngeal
RT-PCR: Reverse Transcriptase Real-Time Polymerase chain reaction
PK: Pharmacokinetic
SAE: Serious adverse event
SARS: Severe Acute Respiratory Syndrome
SARS-CoV-2: Severe Acute Respiratory Syndrome Coronavirus 2
TACO: Transfusion-associated circulatory overload
T. cruzi: *Trypanosoma cruzi*
TRALI: Transfusion-related acute lung injury
UP: Unanticipated Problem
UPnonAE: Unanticipated Problem that is not an Adverse Event
ZIKV: Zika virus

1. Background and scientific rationale

Beyond supportive care, there are currently no proven treatment options for coronavirus disease (COVID-19) and the related pneumonia, the infection caused by Severe Acute Respiratory Syndrome Coronavirus 2 (SARS-CoV-2). Human convalescent plasma is an option for treatment of COVID-19 and could be rapidly available when there are sufficient numbers of people who have recovered and can donate high titer neutralizing immunoglobulin-containing plasma.

Passive antibody therapy involves the administration of antibodies to a given agent to a susceptible individual for the purpose of preventing or treating an infectious disease due to that agent. In contrast, active vaccination requires the induction of an immune response that takes time to develop and varies depending on the vaccine recipient. Some immunocompromised patients fail to achieve an adequate immune response. Thus, passive antibody administration is the only means of providing immediate immunity to susceptible persons and immunity of any measurable kind for highly immunocompromised patients.

Passive antibody therapy has a storied history going back to the 1890s and was the only means of treating certain infectious diseases prior to the development of antimicrobial therapy in the 1940s (1,2). Experience from prior outbreaks with other coronaviruses, such as SARS-CoV-1 shows that such convalescent plasma contains neutralizing antibodies to the relevant virus (3). In the case of SARS-CoV-2, the anticipated mechanism of action by which passive antibody therapy would mediate protection is viral neutralization. However, other mechanisms may be possible, such as antibody dependent cellular cytotoxicity and/or phagocytosis. Convalescent serum was also used in the 2013 African Ebola epidemic. A small non-randomized study in Sierra Leone revealed a significant increase in survival for those treated with convalescent whole blood relative to those who received standard treatment (4).

The only antibody type that is currently available for immediate use is that found in human convalescent plasma. As more individuals contract COVID-19 and recover, the number of potential donors will continue to increase.

A general principle of passive antibody therapy is that it is more effective when used for prophylaxis than for treatment of disease. When used for therapy, antibody is most effective when administered shortly after the onset of symptoms. The reason for temporal variation in efficacy is not well understood but could reflect that passive antibody works by neutralizing the initial inoculum, which is likely to be much smaller than that of established disease. Another explanation is that antibody works by modifying the inflammatory response, which is also easier during the initial immune response, which may be asymptomatic (5). As an example, passive antibody therapy for pneumococcal pneumonia was most effective when administered shortly after the onset of symptoms and there was no benefit if antibody administration was delayed past the third day of disease (6). ***In this context, we seek to treat patients who are sick***

enough to warrant hospitalization prior to the onset of overwhelming disease including a systemic inflammatory response, sepsis, and/or ARDS.

For passive antibody therapy to be effective, a sufficient amount of antibody must be administered. When given to a susceptible person, this antibody will circulate in the blood, reach tissues and provide protection against infection. Depending on the antibody amount and composition, the protection conferred by the transferred immunoglobulin can last from weeks to months.

2. Experience with the use of convalescent plasma against coronavirus diseases

In the 21st century, there were two other epidemics with coronaviruses that were associated with high mortality, SARS1 in 2003 and MERS in 2012. In both outbreaks, the high mortality and absence of effective therapies led to the use of convalescent plasma. The largest study involved the treatment of 80 patients in Hong Kong with SARS (7). **Patients treated before day 14 had improved prognosis defined by discharge from hospital before day 22, consistent with the notion that earlier administration is more likely to be effective.** In addition, those who were RT-PCR positive and seronegative for coronavirus at the time of therapy had improved prognosis. There is also some anecdotal information on the use of convalescent plasma in seriously ill individuals. Three patients with SARS in Taiwan were treated with 500 ml of convalescent plasma, resulting in a reduction in plasma virus titer and each survived (8). Three patients with MERS in South Korea were treated with convalescent plasma, but only two of the recipients had neutralizing antibody in their plasma (9). The latter study highlights a challenge in using convalescent plasma, namely, that some who recover from viral disease may not have high titers of neutralizing antibody (10). Consistent with this point, an analysis of 99 samples of convalescent sera from patients with MERS showed that 87 had neutralizing antibody with a geometric mean titer of 1:61. This suggests that antibody declines with time and/or that few patients make high titer responses. *The plasma product we administer will be collected 14-21 days after symptom resolution and antibody titers will be assessed. We will confirm clearance by at least 1 negative NP swab at the time of collection for NA titer assessment. If NA titers are high enough, at the time of plasma collection, a second NP can be done (potentially) to further confirm that the donor is not viremic. Otherwise the donor will fulfill all of the standard donor criteria.*

It is also possible that other types of non-neutralizing antibodies are made that contribute to protection and recovery as described for other viral diseases (11). There are reports that convalescent plasma was used for therapy of patients with COVID-19 in China during the current outbreak (http://www.xinhuanet.com/english/2020-02/28/c_138828177.htm). Although few details are available from the Chinese experience and published studies involved small numbers of patients, the available information suggests that convalescent plasma administration reduces viral load and was safe.

3. Known potential risks

- a. The theoretical risk involves the phenomenon of antibody-mediated enhancement of infection (ADE). ADE can occur for several viral diseases and involves an enhancement of disease in the presence of certain antibodies. For coronaviruses, several mechanisms for ADE have been described and there is the theoretical concern that antibodies to one type of coronavirus could enhance infection to another viral strain (12). It may be possible to predict the risk of ADE of SARS-CoV-2 experimentally, as proposed for MERS. Since the proposed use of convalescent plasma in the COVID-19 epidemic would rely on preparations with high titers of neutralizing antibody against the same virus, SARS2-CoV-2, ADE may be unlikely. The available evidence from the use of convalescent plasma in patients with SARS1 and MERS (13) and anecdotal evidence of its use in patients with COVID-19 (http://www.xinhuanet.com/english/2020-02/28/c_138828177.htm), suggest it is safe. Nevertheless, caution and vigilance will be required in for any evidence of enhanced infection.
- b. Another theoretical risk is that antibody administration to those exposed to SARS-CoV-2 may avoid disease but modify the immune response such that those individuals mount attenuated immune responses, which would leave them vulnerable to subsequent re-infection. In this regard, passive antibody administration before vaccination with respiratory syncytial virus was reported to attenuate humoral but not cellular immunity (14). This concern could be investigated as part of a clinical trial by measuring immune responses in those exposed and treated with convalescent plasma to prevent disease. If the concern proved real these individuals could be vaccinated against COVID-19 when a vaccine becomes available. *These concerns seem modest compared to the possibility of limiting the duration and severity of disease, and avoiding interventions like mechanical ventilation, ARDS and sepsis.*
- c. Finally, there are risks associated with any transfusion of plasma including transmission of transfusion transmitted viruses (e.g. HIV, HBV, HCV, etc.), allergic transfusion reactions, anaphylaxis to transfusion, febrile transfusion reaction, transfusion related acute lung injury (TRALI), transfusion associated cardiac overload (TACO), and hemolysis should ABO incompatible plasma be administered. In order to minimize the risks of disease transmission, pathogen reduction techniques will be utilized to prepare the plasma. In addition, donors will fulfill donor requirements for whole blood donation and frequent apheresis plasma donation with the exception of recent illness, in this case COVID-19 infection.

4. Known potential benefits

A key potential benefit is treatment for established infection. Convalescent plasma would be administered to those with clinical disease in an effort to reduce their symptoms and mortality. Based on the historical experience with antibody administration, it can be anticipated that *antibody administration relatively early in the*

course of disease would more effective in preventing disease progression than in the treatment of established severe disease.

Given that historical and current anecdotal data on use of convalescent plasma suggest it is safe in coronavirus infection, the high mortality of COVID-19, particularly in elderly and vulnerable persons, suggests that the benefits of its use in those at high risk for or with early disease outweigh the risks. However, for all cases where convalescent plasma administration is considered, a risk-benefit assessment must be conducted to assess individual variables.

Investigational plan

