4.1 Study Objectives

Primary Efficacy Objective:

Preliminary evaluation the efficacy of treatment with high-titer Anti- SARS-CoV-2 plasma versus control (standard plasma) in patients with COVID-19 respiratory symptoms.

Primary Safety Objective:

Evaluate the safety of treatment with high-titer anti-SARS-CoV-2 plasma versus control (standard plasma) in patients with COVID-19 respiratory symptoms.

Secondary Objectives:

Compare the anti-SARS-CoV-2 convalescent plasma and control (standard plasma) groups anti-SARS-CoV-2 titers at days 0, 1, 3, 7 and 14 (additional days 21 and 28 may be included, as available).

Compare the rates, levels and duration of SARS-CoV-2 RNA in NP swabs using RT-PCR amongst the anti-SARS-CoV-2 convalescent plasma and control (standard plasma) groups at days 0, 7 and 14. Other specimen types may be tested as available (*eg.*, BAL fluid, tracheal secretions, sputum, etc.) or when RT-PCR assays are validated for additional sources (*i.e.*, stool, blood).

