7.1.2 Analysis of anti-SARS-CoV-2 titers

Analysis of titers will also primarily be descriptive, comparing the geometric mean titers at days 0, 1, 3, 7 and 14 between the randomized arms.

8. Endpoints

Primary Endpoint: Avoidance of new or ongoing ICU admission.

Secondary endpoints:

1. Cardio-circulatory arrest (at any time)
2. Transfer to ICU
3. Type and duration of respiratory support (and other ICU support) in ICU
4. ICU mortality and LOS
5. Hospital mortality and LOS
6. Ventilator-free days
7. 60 day mortality

Primary Safety Endpoints:

- Rapid deterioration of respiratory or clinical status on transfusion of SARS-CoV-2 convalescent plasma
- Cumulative incidence of serious adverse events during the study period: transfusion reaction (fever, rash), transfusion related acute lung injury (TRALI), transfusion associated circulatory overload (TACO), transfusion related infection

Secondary Endpoints

1. Anti-SARS-CoV-2 titers at days 0, 1, 3, 7 and 14.
2. Rates and duration of SARS-CoV-2 PCR positivity (RT-PCR) at days 0, 3, 7, and 14.

9. Study procedures

Day -1 to 0:

- A. Screening (must be completed before randomization)
- B. Subject informed consent (obtained before performing study related activities)
- C. Baseline Evaluation (at screening) (much of the information will be obtained from the medical record)
 1. Demographics (Age, sex ethnicity, race)
 2. Medical history (timing of exposure to COVID-19 source patient, acute and chronic medical condition, medications, allergies. Any medical condition arising after consent should be recorded as AE)
 3. COVID-19 symptom screen (fevers, cough, shortness of breath), onset of symptoms, source of contagion
 4. Vital signs
 5. COVID-19 testing (RT-PCR) from nasopharyngeal, throat, tracheal aspirate or broncho alveolar lavage and stool (optional) samples
 6. Blood typing, CBC, comprehensive metabolic panel
 7. Serological testing: anti-SARS CoV-2 titers
 8. Stored samples for future studies
 9. Urine or serum pregnancy test for females of childbearing potential. Results from laboratory tests obtained up to 7 days before enrollment may be used for the pregnancy test.
 10. Determination of eligibility as per inclusion/exclusion criteria age, consent, positive for COVID-19, respiratory symptoms, not already an ICU patient,, between day 3 and 7 of first sign of illness (or within 72 hours of admission)

DAY 0:

1. Randomization of eligible subjects

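### ICU admission measures the Summary's objective on oxygenation and ventilation support only indirectly, and no listed efficacy endpoint captures escalation of oxygen support on the ward

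*Protocol*

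**What the plan says.** The Summary gives the efficacy aim as "Primary Efficacy Objective: Reduction in progression of oxygenation and ventilation support" and directly below it "Primary Endpoint: Avoidance of ICU admission". Section 8 words the endpoint as "Primary Endpoint: Avoidance of new or ongoing ICU admission". Section 4.1 states the primary efficacy objective in general terms, "Preliminary evaluation the efficacy of treatment with high-titer Anti- SARS-CoV-2 plasma versus control", without mentioning oxygenation or ventilation.

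Two secondary endpoints concern respiratory support. One is "Type and duration of respiratory support (and other ICU support) in ICU", which is restricted to the ICU in the Summary, in section 8 and in section 10. The other is "Ventilator-free days", which carries no such restriction.

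The Summary's list of items to be assessed in all subjects also names outcome measures: a rise in oxygen requirement, judged by an oxygenation ratio, and the oxygen strategy, graded from nasal cannula up to ECMO. Neither appears in any of the three endpoint lists. A 7-point ordinal scale is scheduled repeatedly (Schedule of Events; section 9). The seven items in section 10 under the ordinal-scale label are essentially the efficacy endpoints again, not graded levels of support.

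**The concern.** The objective is about the level of support and the primary endpoint is about the place of care. The two are related but can disagree. A patient who moves from nasal cannula to high-flow oxygen and stays on the ward has progressed in the sense of the objective, yet counts as a success on the primary endpoint and contributes nothing to secondary endpoint 3.

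The trial could thus report on ICU admission without answering its stated question. If the support endpoint were compared only among patients who reached the ICU, the groups compared would have been selected by an event that occurs after randomisation and is itself the primary outcome. Such a comparison is no longer protected by randomisation.

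**Working it through.** The protocol has no figure to reproduce here: it gives a sample size of 20 without a planning event rate. The check compares the places that state an objective, an endpoint or a measure.

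| Place | What it covers | Captures oxygen escalation on the ward? |
|---|---|---|
| Primary endpoint (Summary, section 8) | ICU admission | No |
| Secondary endpoint 3 (Summary, sections 8 and 10) | Support in ICU | No |
| Secondary endpoint 6 (same places) | Ventilator-free days, any location | Ventilation part only |
| Outcome measures in all subjects (Summary) | Oxygen requirement, oxygen strategy | Yes, but not listed as an endpoint |
| 7-point scale (Schedule of Events, sections 9 and 10) | Levels not defined | Cannot be determined |

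The measure that fits the objective is therefore planned for all subjects but missing from the endpoint lists.

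**Can escalation happen outside the ICU?** Screening in section 9 excludes patients already in the ICU, so every patient starts elsewhere. Figure 1 appears to place the first oxygen support and nasal cannula in the ward columns, although the column alignment is hard to read. Both points suggest that early progression occurs where endpoint 3 does not look.

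**Two readings of endpoint 3.**
1. Only ICU patients are compared. The comparison then conditions on a post-randomisation event.
2. All patients are included and those never in the ICU count as having no ICU support. The conditioning disappears, but a ward patient on high-flow oxygen is scored like a patient on none.

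Neither reading measures the stated objective.

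**Illustration of size.** Inputs are 10 patients per arm (section 7.1) and an ICU rate p = 0.23 (Figure 1, a published background figure and not a planning assumption of this trial).
- Expected patients per arm with ICU support data: 10 × 0.23 = 2.3. Patients without: 10 − 2.3 = 7.7.
- Chance that an arm has 0 or 1 such patients: 0.77^10 + 10 × 0.23 × 0.77^9 = 0.073 + 0.219 = 0.292, about 29%.
- The rate in this population is unknown. At half the background rate the expectation is 10 × 0.115 = 1.15 per arm, and at twice the rate 10 × 0.46 = 4.6.

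Over this range, less than half of each arm would be expected to contribute ICU support data.

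**The case against.** The strongest reply is that ICU admission was chosen on purpose. The text under Figure 1 names avoiding ICU admission as the goal, and section 11 links progression to both ICU admission and aggressive respiratory support. In a 20-patient phase 1 study this is a defensible marker. That stands, and it is why the primary endpoint need not be replaced.

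A second reply is that no text says endpoint 3 is compared only among ICU patients. Section 7.1 makes the whole arm the default denominator for percentages, and handling of duration could be left to an analysis plan. This also stands: the conditioning problem depends on how the endpoint is read. It does not rescue the endpoint, because under the whole-arm reading ward support is still not counted.

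A third reply is that section 4.1 is merely broader than the Summary. That is fair. The two do not exclude each other, but a primary objective should be stated the same way in both places.

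Finally, a reader might infer that no endpoint measures the objective at all. The protocol does not support this. Ventilator-free days is listed without an ICU limit and covers part of the ventilation component, and the Summary names the oxygenation measures for all subjects.

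**Conclusion.** The point holds as a mismatch that is cheap to repair. The primary endpoint reflects the Summary's objective indirectly, ventilator-free days reflects part of it, and oxygen escalation on the ward is captured by no listed efficacy endpoint even though suitable measures are planned for all subjects.

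The finding rests on the wording of the endpoint lists and not on any event rate. The figure of about 2 of 10 patients per arm is illustrative and moves with the assumed ICU rate. It should not be read as saying that the other patients are ignored altogether, since they contribute to the primary endpoint and to ventilator-free days. Nor do the documents show that ICU admission is a wrong primary endpoint.

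**What to change.** Keep ICU admission as the primary endpoint and make three changes.

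1. In secondary endpoint 3 (Summary, sections 8 and 10), replace the restriction to the ICU by *at any location*.
2. Define the worst respiratory-support level through Day 28 from the Summary's oxygen-strategy categories, with death as the worst level. Compare it between arms in all randomised patients and report it beside ICU admission. Death needs a rank because a patient who dies early could otherwise carry a favourable level.
3. Use one wording of the primary efficacy objective in the Summary and section 4.1.

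The cost is revised text and one further analysis, based on measures the Summary already plans for all subjects. There are two practical limits. First, the levels must be written out: the 7-point scale is not usable as it stands, and the Summary's list lacks a category for no oxygen and mixes in rescue items, such as corticosteroids, that are not levels of support. Second, support after discharge may be known only from the Day 28 telephone contact described in section 9, so the plan should say how the level is assigned for that period.
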